1. SCHEMA

2. BACKGROUND AND RATIONALE

2.1 Disease Background

RCC arises from the renal parenchyma and accounts for 90% of all kidney cancer¹. In 2015, there were an estimated 61,500 new cases of kidney cancer in the United States and $\geq 14,000$ deaths. RCC is a heterogeneous disease divided into two major classifications: clear-cell disease which accounts for 80% of all RCC cases and non-clear cell disease.

An increased understanding of the pathogenesis of RCC has changed the landscape of advanced disease management and has shifted the paradigm for front-line treatment. The previous use of cytokines, has largely been replaced by therapies that target vascular endothelial growth factor (VEGF), mammalian target of rapamycin (mTOR), and most recently checkpoint inhibitors. Currently, nine agents have demonstrated efficacy in large phase III clinical trials in metastatic RCC: sunitinib, pazopanib, sorafenib, axitinib, bevacizumab (in combination with IFN- α), temsirolimus, everolimus, and most recently nivolumab and cabozantinib (Table 1).

Table 1. Randomized phase III trials of treatments in metastatic RCC.

Trial	Treatment	#	OS			PFS			ORR		
			Median (months)	HR (95%CI)	P value	Median (months)	HR (95%CI)	P value	%		
First-Line Setting											
Motzer et al (2007; 2009) ^{2,3}	Sunitinib	375	26.4	0.82 (0.67-1.00)	0.051	11	0.54 (0.45-0.64)	<0.001	47%		
	IFN- α	375	21.8			5			12%		
Escudier et al (2007; 2010) ^{4,5}	Bevacizumab + IFN- α	327	23.3	0.86 (0.72-1.04)	0.129	10.2	0.61 (0.51-0.73)	<0.001	31%		
	IFN- α	322	21.3			5.4			13%		
Rini et al (2002; 2010) ^{6,7}	Bevacizumab + IFN- α	369	18.3	0.86 (0.73-1.01)	0.069	8.5	0.71 (0.61-0.83)	<0.001	26%		
	IFN- α	363	17.4			5.2			13%		
Sternberg et al (2010; 2013) ^{8,9}	Pazopanib	290	22.9	0.91 (0.71-1.16)	0.224	9.2	0.46 (0.34-0.62)	<0.001	30%		
	Placebo	145	20.5			4.2			3%		
Hudes et al (2007) ¹⁰	Temsirolimus	209	10.9	0.73 (0.58-0.92)	0.008	3.8	0.73 (0.58-0.92)	<0.001	8.6%		
	Temsirolimus + IFN- α	210	8.4			3.7			0.96 (0.76-1.20)	0.70	8.1%
	IFN- α	207	7.3			1.9					4.8%

Motzer et al (2013, 2014) ^{11,12}	Sunitinib	553	29.1	0.92 (0.79-1.06)	0.24	9.5	1.05 (0.90-1.22)	NR	25%
	Pazopanib	557	28.3			8.4			31%
Second-Line Setting									
Escudier et al (2007, 2009) ^{13,14}	Sorafenib	451	17.8	0.88 (0.74-1.04)	0.146	5.5	0.44 (0.35-0.55)	<0.01	10%
	Placebo	452	15.2			2.8			2%
Motzer et al (2008, 2010) ^{15,16}	Everolimus	272	14.8	0.87 (0.65-1.15)	0.162	4.0	0.30 (0.22-0.40)	<0.001	1%
	Placebo	138	14.4			1.9			0%
Rini et al (2011, 2013) ^{17,18}	Axitinib	361	20.1	0.969 (0.800-1.174)	0.374	6.7	0.655 (0.55-0.812)	<0.001	19%
	Sorafenib	362	19.2			4.7			9%
Motzer et al (2015) ¹⁹	Nivolumab	406	25.0	0.73 (0.57-0.93)*	0.002	4.6	0.88 (0.75-1.03)	0.11	25%
	Everolimus	397	19.6			4.4			5%
Choueiri et al (2015) ²⁰	Cabozantinib	330	NR	0.67 (0.51-0.89)	0.005	7.4	0.58 (0.45-0.75)	<0.001	21%
	Everolimus	328	NR			3.8			5%

HR=hazard ratio, IFN- α =interferon-alpha, NR=not recorded, ORR=objective response rate, OS=overall survival, PFS=progression-free survival.

*98.5% confidence interval.

The efficacy of nivolumab was demonstrated in a phase III, open-label, randomized trial comparing nivolumab with everolimus in patients with metastatic RCC having received previous treatment.²¹ Treatment with nivolumab resulted in an improved OS compared to everolimus (Table 1). From this study, objective responses were observed in 25% of patients treated with nivolumab: CR 1% and PR 24%. The median time to response was 3.5 months (range 1.4-24.8 months) in the 103 patients with a response to nivolumab. The median duration of response was 12.0 months (range 0-22.2 months) in responders. The rate of SD and PD as best response were 34% and 35%, respectively.

As demonstrated, individual patient responses to treatment are heterogeneous. A minor portion of patients experience an objective response. Given the heterogeneity of response to treatment, there is a critical need to tailor treatment recommendations to the individual needs of the patient. At the present, it is not clear if treatment with nivolumab can be discontinued in patients with an ORR and result in persistent disease response. Furthermore, in patients who do not experience a response to therapy, can further checkpoint inhibition with ipilimumab convert SD or PD to an objective response. Phase I data suggest that nivolumab combined with ipilimumab has demonstrated substantially greater clinical activity as measured by ORR than either agent alone. This question is currently being answered in a phase III, open label study of nivolumab combined with ipilimumab versus sunitinib in patients with previously untreated advanced RCC (CheckMate214). In this study, we propose to investigate a response-based approach to treatment with nivolumab in patients with metastatic RCC.

2.2 Nivolumab

Programmed death receptor-1 (PD-1, CD279), a 55 kD type I transmembrane protein, is a member of the CD28 family of T-cell costimulatory receptors that also includes CD28, CTLA-4, ICOS, and BTLA. PD-1 contains an intracellular membrane proximal immunoreceptor tyrosine inhibitory motif (ITIM) and a membrane distal immunoreceptor tyrosine-based switch motif (ITSM). Two ligands specific for PD-1 have been identified: PD-L1 (B7-H1/CD274) and PD-L2 (B7-DC/CD273). PD-L1 and PD-L2 have been shown to down-regulate T-cell activation upon binding to PD-1 in both murine and human systems^{22, 23}. PD-1 delivers a negative signal by the recruitment of a protein tyrosine phosphatase SHP-2 to the phosphorylated tyrosine residue in the ITSM in its cytoplasmic region^{24, 25}. PD-1 is primarily expressed on activated T cells, B cells and myeloid cells²⁶.

Nivolumab is a fully human, IgG4 (kappa) isotype, mAb that binds PD-1. Blockade of the PD-1 pathway by nivolumab was studied using the mixed lymphocyte reaction (MLR). PD-1 blockade resulted in a reproducible enhancement of both proliferation and IFN- γ release in the MLR.

Nivolumab monotherapy has been studied in subjects with RCC. In a phase 1 dose escalation followed by dose expansion study, the safety and clinical activity of nivolumab was investigated²⁷. A total of 34 patients with previously treated RCC were enrolled between 2008 and 2012 and received nivolumab (1-10 mg/kg) in an outpatient setting once every 2 weeks for up to 96 weeks. Ten patients (29%) achieved an objective response by RECIST 1.0 with median response duration of 12.9 months. Nine additional patients (27%) demonstrated SD lasting > 24 weeks. Three of five patients who stopped treatment while in response continued to respond for \geq 45 weeks. Median OS in all patients (71% with 2-5 prior lines of therapy) was 22.4 months. And the 1, 2, and 3 year survival rates were 71%, 48%, and 44%. Grade 3-4 treatment-related adverse events (AEs) occurred in 18% of patients and all were reversible.

In a phase II study, 168 patients with clear cell RCC who received at least one prior anti-angiogenic therapy (70% received \geq 2 prior systemic therapy regimens) were randomized to receive nivolumab 0.3 mg/kg (n=60), 2 mg/kg (n=54), and 10 mg/kg (n=54).²¹ Median PFS was 2.7 months, 4.0 months, and 4.2 months at 0.3, 2, and 10 mg/kg respectively. The median OS was 18.2 months, 25.5 months, and 24.7 months, respectively. The ORR ranged from 20-22% across dose levels.

Most of the 167 patients (n=122, 73%) experienced treatment-related AEs (any grade) and 19 patients (11%) experienced grade 3-4 treatment-related AEs. The incidence of treatment-related AEs of any grade was similar across the dose arms: 75%, 67%, and 78% in the 0.3, 2, and 10 mg/kg respectively. Grade 3-4 events occurred in 5%, 17%, and 15%, respectively. The most common any grade treatment-related AEs were fatigue, nausea, pruritis, rash, decreased appetite, diarrhea, dry mouth, arthralgia, dry skin, and hypersensitivity. Systemic corticosteroids were administered in 9 (15%), 10 (19%), and 18 (33%) patients in the 0.3, 2, and 10 mg/kg arms, respectively. Treatment-related AEs leading to discontinuation of study drug occurred in 7% (n=11), the most common reason being elevated serum aspartate aminotransferase (AST), occurring in two patients.

The efficacy of nivolumab in RCC was demonstrated in a randomized, open-label, phase III study of nivolumab compared to everolimus in patients with RCC who had received previously treatment.¹⁹ In this study, a total of 821 patients with advanced clear cell RCC were randomized 1:1 to received 3 mg/kg of nivolumab IV every 2 weeks of 10 mg of everolimus orally. The primary endpoint was OS.

The median OS was 25.0 months (95% CI 21.8 to NR) with nivolumab and 19.6 months (95% CI 17.6-23.1) with everolimus (HR 0.73, 95% CI 0.57-0.93, p=0.002). The ORR was 25% in the nivolumab arm and 5% in the everolimus arm (OR 5.98, 95% CI 3.68-9.72, p<0.001). PR were observed in 99 patients (24%) in the nivolumab group and in 20 patients (5%) in the everolimus group. CR were observed in 4 patients (1%) in the nivolumab group and 1 patient (<1%) in the everolimus group. The median time to response was 3.5 months (range 1.4-24.8 months) among the 103 patients with a response in the nivolumab group and 3.7 months (range 1.5-11.2 months) among the 22 patients with a response in the everolimus group. The median duration of response was 12 months (range 0-27.6 months) in the nivolumab group and 12 months (0-22.2 months) with everolimus. The median PFS was 4.6 months (95% CI 3.7-5.4) with nivolumab and 4.4 months (95% CI 3.7-5.5) with everolimus (HR 0.88, 95% CI 0.75-1.03, p=0.11).

Treatment-related AEs of any grade occurred in 319 of the 406 patients (79%) treated with nivolumab and in 349 of the 397 patients (88%) treated with everolimus. The most common treatment-related AEs among patients who received nivolumab were fatigue (134 patients, 33%), nausea (57 patients, 14%), and pruritus (57 patients, 14%); among patients who received everolimus, the most common events were fatigue (134 patients, 34%), stomatitis (117 patients, 29%), and anemia (94 patients, 24%). Grade 3 or 4 treatment-related AEs occurred in 76 of the 406 patients (19%) treated with nivolumab and in 145 of the 397 patients (37%) treated with everolimus; the most common grade 3 or grade 4 event was fatigue (10 patients, 2%) with nivolumab and anemia (31 patients, 8%) with everolimus. Treatment-related adverse events leading to treatment discontinuation occurred in 31 of the 406 patients (8%) treated with nivolumab and in 52 of the 397 patients (13%) treated with everolimus.

2.3 Ipilimumab

Cytotoxic T-Lymphocyte Antigen 4 (CTLA-4), an activation-induced T-cell surface molecule, is a member of the CD28:B7 immunoglobulin superfamily that competes with CD28 for B7. CTLA-4-mediated signals are inhibitory and turn off T cell-dependent immune responses^{28, 29}.

Ipilimumab is a fully human monoclonal IgG1 κ that binds to the CTLA-4 antigen expressed on a subset of T cells from human and nonhuman primates. The proposed mechanism of action for ipilimumab is interference of the interaction of CTLA-4 with B7 molecules on antigen presenting cells (APCs), with subsequent blockade of the inhibitory modulation of T-cell activation promoted by the CTLA-4/B7 interaction.

Ipilimumab monotherapy for the treatment of metastatic RCC was studied in a phase 2 clinical trial. Two sequential cohorts were studied, each with a loading dose of 3 mg/kg followed by 3 doses of either 1 mg/kg (group 3-1; n = 21) or 3 mg/kg (group 3-3; n = 40). Subjects with stable disease or partial or complete response were allowed additional treatment. In group 3-1 (n = 21), one subject (5%) had a PR. In group 3-3 (n = 40), 5 subjects (12.5 %) had a PR. Among 14

treatment-naive subjects in group 3-3, 3 (21%) had a PR. The major toxicities were colitis (all grade 3-4; 14% in group 3-1, 33% in group 3-3) and hypophysitis (1 grade 3-4, 1 grade 1-2 in group 3-3; none in group 3-1). Most reported AEs were grade 1-2 (57% in group 3-1, 35% in group 3-3) or grade 3 (38% in group 3-1, 48% in group 3-3). There were 6 subjects (15%) with grade 4 AEs in group 3-3. The most common treatment-related AEs in group 3-1 (total 81%) and group 3-3 (total 93%) were diarrhea (38% and 40%, respectively) and fatigue (33% and 38%, respectively). Most AEs were manageable with appropriate treatment, including high dose corticosteroids and hormone replacement.

2.4 Nivolumab and Ipilimumab

Preclinical data indicate that the combination of PD-1 and CTLA-4 receptor blockade may improve antitumor activity. In vitro combinations of nivolumab plus ipilimumab increase IFN- γ production 2- to 7-fold over either agent alone in a mixed lymphocyte reaction. Increased antitumor activity of the combination was also observed in 3 of 5 syngeneic murine cancer models. In a murine melanoma vaccine model, blockade with either CTLA-4 or PD-1 antibodies increased the proportion of CTLA-4 and PD-1-expressing CD4/CD8 tumor infiltrating T effector cells, and dual blockade increased tumor infiltration of T effector cells and decreased intratumoral T regulatory cells, as compared to either agent alone³⁰.

A phase I study investigated the safety and activity of nivolumab and ipilimumab in RCC³¹. Subjects with metastatic RCC (favorable/intermediate Memorial Sloan Kettering Cancer Center (MSKCC) score; Karnofsky performance status \geq 80%; untreated or any number of prior therapies) were randomized to receive nivolumab 3 mg/kg + ipilimumab 1 mg/kg (arm N3 + I1) or nivolumab 1 mg/kg + ipilimumab 3 mg/kg (arm N1 + I3) IV every 3 weeks for 4 doses then nivolumab 3 mg/kg IV every 2 weeks until progression/toxicity. The primary objective was to assess safety/tolerability and the secondary objective was to assess antitumor activity. Subjects were randomized to N3 + I1 (n = 21) and N1 + I3 (n = 23). Most patients (n=34; 77%) had prior systemic therapy (N3 + I1: 16; N1 + I3: 18). The confirmed ORR was 43% (N3 + I1) and 48% (N1 + I3). Duration of response was 4.1+ to 42.1+ weeks (7 of 9 responses ongoing) in N3 + I1, and 12.1+ to 35.1+ wks (9 of 11 responses ongoing) in N1 + I3. Best response of SD was seen in 5 (24%) patients (N3 + I1) and 8 (35%) pts (N1 + I3). Median PFS was 36.6 weeks (N3 + I1) and 38.3 weeks (N1 + I3). These data are still immature, with 11 of 21 events reported for N3 + I1 and 10 of 23 events reported for N1 + I3.

The safety of nivolumab combined with ipilimumab was assessed in the phase 1 study.

Treatment-related AEs were seen in 39/44 patients (89%), including 16/21 (76.2%) in N3 + I1 and 23/23 (100%) in N1 + I3. Across the N3 + I1 and N1 + I3 arms, the most common (\geq 20%) treatment related AEs of any grade were fatigue (61%), diarrhea (32%), nausea (30%), rash (27%), pruritis (25%), ALT increased (23%), AST increased (20%), hypothyroidism (20%), and lipase increased (20%). Grade 3-4 related AEs occurred in 19 patients (29%), including 6/21 (29%) at N3 + I1 and 14/23 (61%) at N1 + I3. The most common (\geq 5%) drug-related grade 3-4 events were lipase increased (21%), ALT increased (14%), AST increased (7%), diarrhea (9%), fatigue (5%), amylase increased (5%), colitis (5%), lymphocyte count decreased (5%). No grade 3-4 pneumonitis was seen. No treatment-related deaths were reported.

Treatment-related AEs (including Grade 3-4), treatment-related AEs leading to discontinuation, and treatment-related SAEs all occurred more commonly in subjects in the N1 + I3 arm than in the N3 + I1 arm: treatment related AEs 76.2% N3 + N1 versus 100% N1 + I3; treatment related grade 3-4 AEs 28.6% versus 60.9%, treatment related AEs leading to discontinuation 9.5% versus 26.1%.

2.5 Rationale

Patients with metastatic RCC have multiple treatment options however the only one currently demonstrated to improve OS is nivolumab. Little information is known about whether treatment can safely be discontinued in patients who experience a response. Data from early drug trials of nivolumab suggest that some patients who discontinued therapy while demonstrating a response continue to derive benefit from therapy for a durable period of time. This study will plan to formally investigate this question. Nivolumab 3 mg/kg combined with ipilimumab 1 mg/kg has demonstrated substantial clinical activity, as measured by ORR, while still exhibiting an acceptable safety profile. Given the promising data of the combination of nivolumab and ipilimumab, this study will investigate whether ipilimumab can be used to improve ORR for patients who experience SD or PD initially. In this study, we are evaluating the efficacy of nivolumab when given in combination with a total of 2 doses of ipilimumab every 3 weeks (\pm 3 days). The efficacy of 2 doses compared to 4 doses of ipilimumab when given in combination with nivolumab is unknown. Furthermore, the efficacy of re-treatment with nivolumab combined with ipilimumab is unknown. Studies exploring differing treatment schedules are lacking in RCC. The responses induced by immunotherapy are expected to be more durable than those induced by VEGF receptor therapy, and are therefore likely to translate into improvements OS, as seen with nivolumab alone.

2.6 Correlative Studies Background

PD-L1/PD-1 pathway activation in tumors, as determined by PD-L1 levels, may be an important predictive diagnostic for checkpoint inhibition. Published results suggest that expression of PD-L1 in tumors correlates with response to anti-PD-1 therapy³². This correlation was also observed with nivolumab in data from the phase II study of nivolumab alone. Tumor specimens (collected from baseline fresh tumor specimens) from patients meeting eligibility criteria will be tested for PD-L1 expression and other markers of immunogenicity and angiogenesis. In addition, PD-L1 status (as defined by expression of PD-L1 on tumor cells or TIMC) will be correlated with outcomes. Because the expression of PD-L1 on the surface of both tumor cells and TIMC can be a dynamic process and because PD-L1 expression on these cells may vary between primary and metastatic sites, mandatory fresh tumor specimens will be collected at baseline. Additionally, to investigate mechanisms of acquired resistance to therapy, we will obtain progression biopsies. For patients in Arm A who experience an initial CR/PR to nivolumab alone, we will obtain an optional biopsy at time of progression prior to re-initiation of nivolumab. From patients who demonstrate progression to nivolumab and ipilimumab we will obtain an optional tumor biopsy at progression on both agents.

Changes in biomarkers in the blood may provide evidence for the biological activity of nivolumab alone or in combination with ipilimumab in humans and may allow for the development of a blood based biomarkers to help predict which patients may benefit from therapy. A secondary objective is to assess the immunomodulatory properties of nivolumab alone or in

combination with ipilimumab by evaluating baseline levels and changes in levels upon treatment of surrogate pharmacodynamic markers in the blood. In addition, we will correlate levels with the anti-tumor activity of the combination of these agents.

2.7 Study Design

This is a phase II study investigating a response-based approach to therapy with nivolumab and ipilimumab in subjects with advanced renal cell carcinoma (RCC). All subjects will initiate therapy with nivolumab. After 8 weeks (± 7 days), subjects will undergo the first response assessment, as well as additional assessments for the response confirmations if applicable, then be assigned to the study arms A and B. Confirmation scans for patients with CR/PR/SD will occur following an additional 8 weeks (± 7 days). For patients with PD, initial confirmation scans will be obtained at 4 weeks (± 7 days) at the discretion of the treating investigator if the patient is stable to wait for confirmatory imaging. Arm allocation will occur within the first 6 months of the study. For subjects to be allocated to Arm A, they need to have a confirmed CR/PR on two serial and consecutive imaging assessments within the first 6 months of the study while on nivolumab treatment alone. All other subjects who are not able to demonstrate a persistent confirmed CR/PR within the first 6 months of the study, will be allocated to Arm B.

Single Cell Sequencing Cohort: An additional subset of patients (n=25) will be enrolled to the study at DFCI and selected sites with capability for single cell molecular transcriptomic assessment. These patients will receive the same treatment as detailed above and will be allocated in Arm A and B as detailed above. All patients will undergo a mandatory baseline biopsy. Biopsy schedule by treatment arm is detailed below:

Arm A:

Mandatory biopsy at baseline

Optional biopsy at time of response following discontinuation of nivolumab

Mandatory biopsy at final treatment discontinuation/off study

Arm B:

Mandatory biopsy at baseline

Mandatory biopsy at final treatment discontinuation/off study

Arm A (persistent PR/CR) includes the following patient scenarios:

- Subjects who experience a partial response (PR) or complete response (CR) at 8 weeks (initial response assessment) from initiation of primary nivolumab therapy and who maintain a persistent PR or CR at the subsequent imaging assessment in 8 weeks (± 7 days) (i.e., ~16 weeks from initiation of nivolumab);

OR

- Subjects who experience stable disease (SD) at the initial response assessment at 8 weeks from initiation of primary nivolumab therapy, with the subsequent scan in 8 weeks (± 7 days) documenting CR/PR which is maintained at the next imaging assessment in 8 weeks (± 7 days) (i.e., ~24 weeks from initiation of nivolumab).

Patients who have SD on initial assessment followed by CR/PR on first confirmatory assessment which does not persist on the second confirmatory imaging assessment will be allocated to Arm B as CR/PR was not persistent and confirmed on consecutive imaging assessments.

Subjects with confirmed PR/CR (arm A) will discontinue nivolumab and be followed with serial imaging assessments every 8 weeks. If progressive disease (PD) develops, therapy with nivolumab will be resumed and will not be discontinued if a subsequent PR or CR were to occur. Subjects who experience subsequent PD following re-initiation of nivolumab, will be treated with nivolumab + ipilimumab every 3 weeks x 2 doses and will continue nivolumab. All patients will continue on treatment with nivolumab alone every 4 weeks which will begin 5 weeks \pm 3 days after the last dose of nivolumab + ipilimumab. For subjects who experience a PD on nivolumab and ipilimumab, treatment will be discontinued.

If by 24 weeks, subjects have not demonstrated a persistent CR/PR confirmed on at least two serial scan assessments, then subjects will be allocated to Arm B at the 24 week time point.

Arm B (persistent PD/SD) includes the following patient scenarios:

- Subjects who experience PD at 8 weeks (initial response assessment) on primary nivolumab therapy which is then confirmed by a second scan within 4 weeks (\pm 7 days). The confirmatory scan is not required if the site investigator determines that this is clinically detrimental;
- Subjects who initially experience SD at 8 weeks (initial response assessment), which is confirmed with a second scan showing SD in 8 weeks (\pm 7 days)
- Subjects who have received at least 3 doses of nivolumab and may have signs and/or symptoms concerning for early clinical progression with radiographic evidence of PD before 8 weeks
- Subjects who do not meet the criteria for allocation into Arm A given lack of persistent CR/PR confirmation on serial and consecutive imaging within the first 6 months of the study will be allocated to Arm B by the 6-month time point.

Subjects in Arm B will receive ipilimumab every three weeks x 2 doses in addition to nivolumab. Treatment with nivolumab alone every 4 weeks will begin 5 weeks \pm 3 days after the last dose of nivolumab + ipilimumab. Subjects will be followed with serial imaging assessments every 8 weeks (except the first imaging assessment which will take place at 12 weeks since ipilimumab addition). If PD persists or develops, all treatments will be discontinued. If PR/CR/SD is observed subjects will continue nivolumab.

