- 4: TSH and free T4 will be done at screening and every 2 cycles (8 weeks ± 7 days).
- 5: For women of childbearing potential (WOCBP): urine or serum βhCG. If a urine test is done and it is positive or cannot be confirmed as negative, a serum pregnancy test will be required. WOCBP should be counseled regarding the importance of contraception from the time of screening until 180 days after last dose of study drug(s). If a subject communicates that pregnancy is possible, a serum βhCG should be performed per site investigator's discretion.
- 6: Hepatitis B virus (HBV) serology (HBsAg, antibodies against HBsAg, antibodies against hepatitis B core antigen), and HCV serology (anti-HCV) will be performed. HBV DNA test is required for subjects who have known positive serology for anti HBc. HCV RNA test is required for subjects who have known positive serology for anti HCV.
- 7: Radiology Imaging at screening to include: Diagnostic CT chest and CT or MRI of the abdomen and pelvis and MRI of the brain. If a subject is not able to obtain an MRI, CT imaging with contrast is acceptable. If a subject is not able to receive contrast, CT head without contrast is acceptable. Radiology Imaging during Primary Treatment: Initial scans will be done after 2 cycles (8 weeks +/- 7 days) of nivolumab. Subjects with PR/CR/SD will have confirmatory scans 8 weeks later (+/- 7 days). Confirmatory scans for subjects with PD are not mandatory but may be attained 4 weeks later if clinically feasible (+/- 7 days). Subjects who have two serial consecutive imaging assessments (8 weeks +/- 7 days apart) which demonstrate CR/PR within the first 6 months of study will be allocated to Arm A. All other subjects who do not meet this criteria will enter Arm B by the 6 month time point. Subjects have who signs and/or symptoms concerning for early clinical progression can undergo imaging before 8 weeks (+/- 7 days). In this scenario, if there is evidence of radiographic progression, subjects may be allocated to Arm B immediately, assuming they have received at least 3 doses of nivolumab. For Single Cell Sequencing Cohort MRI or CT of the Brain will not be collected at screening.
- 8: Primary Treatment: Nivolumab will be administered on Day 1 (+/- 3 days) of each 28-day cycle for 2 cycles. After 2 cycles, disease assessment will occur. Nivolumab alone will continue until disease status documented with confirmatory scans (See Footnote 7) or site investigator

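### Section 2.7 gives two cut-offs for Arm B, 24 weeks and 6 months, and an on-window confirming scan can fall between them, so the same scans can lead to different arms

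*Combined protocol and SAP*

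**What the plan says.** **The 24-week limit.** One sentence of Section 2.7 sends subjects to Arm B under this rule: "If by 24 weeks, subjects have not demonstrated a persistent CR/PR confirmed on at least two serial scan assessments, then subjects will be allocated". The same sentence fixes the moment: "then subjects will be allocated to Arm B at the 24 week time point". It mentions no scan window.

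**The 6-month limit.** The opening paragraph of Section 2.7 says of Arm A candidates that "they need to have a confirmed CR/PR on two serial and consecutive imaging assessments within the first 6 months of the study". It sends the rest to Arm B, describing them as "All other subjects who are not able to demonstrate a persistent confirmed CR/PR within the first 6 months of the study". The last Arm B scenario repeats this: such subjects "will be allocated to Arm B by the 6-month time point". Footnote 7 of the primary-treatment calendar in Section 8 agrees: "All other subjects who do not meet this criteria will enter Arm B by the 6 month time point".

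**The scan route.** "After 8 weeks (± 7 days), subjects will undergo the first response assessment", and the next scan follows 8 weeks (± 7 days) later. The second Arm A scenario in Section 2.7 covers SD at the first scan, followed by a scan "documenting CR/PR which is maintained at the next imaging assessment in 8 weeks", again ± 7 days. The section places that third scan at about 24 weeks from the start of nivolumab.

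**The calendar footnotes.** Footnote 8 keeps subjects on nivolumab alone until confirmatory scans have settled disease status, except where the investigator confirms PD and the subject cannot wait. Footnote 14 moves subjects to an arm calendar once those scans are complete. It assigns the SD-then-CR/PR subject to Arm A if the further scan confirms the response, and names no calendar limit.

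**The concern.** The arm decides the treatment. In Arm A nivolumab stops; in Arm B ipilimumab is added. The arm also decides which primary endpoint the subject contributes to.

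The 24-week limit lies at the centre of the permitted window for the scan that the second Arm A scenario depends on. A subject can follow the schedule exactly, have a confirmed response, and be Arm A under one sentence and Arm B under another. No text says which limit governs, whether the 24-week limit carries the scan window, or when the 6-month clock starts.

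The Arm B analysis is also exposed. Section 3.1.1 speaks of PD/SD subjects who convert, and Section 13.3 describes Arm B as subjects with PD or confirmed SD. The counting rule in Section 13.7.1, however, takes PR or CR in the year from the first ipilimumab dose. Section 10.3.1 measures PR against the baseline sum, and no new baseline at the start of ipilimumab is described. A subject who enters Arm B already in PR could therefore be scored as a response.

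**Working it through.** **Step 1: the dates.** Inputs are from Section 2.7. Days are counted from the first nivolumab dose.

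- Nominal third scan: 3 × 56 = day 168, which is 24 × 7. This reproduces the plan's figure of about 24 weeks.
- Six calendar months: about day 181 to 184, so the two limits are about two weeks apart.
- Second scan on day 112: the third is on window from 112 + 49 = day 161 to 112 + 63 = day 175. Days 169 to 175 lie after day 168, which is 7 of 15 permitted days (47%). None lies after 6 months.
- Each interval runs from the scan before it, so deviations can add up. The extremes are 3 × 49 = day 147 and 3 × 63 = day 189. The latest on-window scans therefore miss the 6-month limit too. If day deviations were uniform and independent (an assumption), about 47% of such schedules would end after day 168 and 1% to 4% after 6 months.

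**Step 2: the clock start.** The 6-month text counts from the study; the scan scenarios count from the start of nivolumab. Section 5.3 allows 14 days between registration and therapy. If the clock started at registration, the 6-month limit could fall as early as 181 − 14 = day 167 to 184 − 14 = day 170 from first dose, which is again inside the scan window.

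**Step 3: one subject, read four ways.** Take SD at week 8, PR on day 112 and PR on day 172.

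| Text | Arm |
|---|---|
| Section 2.7, second Arm A scenario | A |
| Section 2.7 and footnote 7, 6-month limit (counted from first dose) | A |
| Footnotes 8 and 14 | A |
| Section 2.7, 24-week sentence read as day 168 | B |

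**Step 4: the Arm B rule.** Inputs are from Section 13.3: 20 subjects in the first stage, go on with 2 or more responses, 57 in total, success with 6 or more.

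P(success) = Σ from x = 2 to 20 of P(Bin(20, p) = x) × P(Bin(37, p) ≥ 6 − x)

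- p = 0.05: 4.76% (plan: 4.7%). Early stop, P(Bin(20, 0.05) ≤ 1) = 73.6% (plan: 73%).
- p = 0.20: 92.1% (plan: 92%).

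The plan's figures reproduce within rounding or truncation. Now let one of the 57 be certain to count as a response, with p = 0.05 for the others.

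- In the second stage: 20 random subjects, then 36, with 5 − x more needed. P(success) = 9.7%.
- In the first stage: 19 random subjects, at least 1 response among them to go on, then 37, with 5 − x more needed. P(success) = 13.4%.

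**Step 5: the Arm A rule.** With 23 subjects and a bar of 5, the rule gives 7.3% at a true rate of 10% and 94.5% at 35% (plan: 7% and >94%). With 22 subjects and the same bar it gives 6.2% and 92.8%. Losing one subject costs Arm A little.

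**The case against.** The strongest reply is that the protocol already protects this subject. Footnotes 8 and 14 make allocation wait for the confirming scan and then assign a confirmed late responder to Arm A. Section 2.7 itself names the SD-then-CR/PR subject for Arm B only when the response fails to persist on the next scan. Section 6 also uses 8-week and 16-week time points for scans that carry ± 7 days, so the 24-week time point may simply mean the third scan with its window. Six 28-day cycles are 24 weeks, so the two limits may have been meant as one milestone. And a hard day-168 limit would defeat the protocol's own second Arm A scenario on nearly half of the permitted days.

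Most of this stands. A reader might infer that the protocol directs confirmed responders to ipilimumab. The documents do not support that: it follows only from a literal day-168 reading, against the footnotes.

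A reader might also try to count affected subjects from the 3.5-month median time to response in Section 2.2 and the 23 subjects expected in Arm A. That is not supported either. The median comes from another trial with dosing every 2 weeks, and the documents do not say how many subjects would have SD at week 8 and first respond at week 16. If sites follow footnotes 8 and 14, the number may be near zero.

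On the analysis, the population wording in Sections 3.1.1 and 13.3 already points towards not counting such a subject. It is not carried into the counting rule in Section 13.7.1.

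The reply does not remove the conflict. It shows a sensible way to read the text, but no sentence says that the footnotes override the 24-week statement, and footnote 7 in the same calendar brings back a calendar limit.

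**Conclusion.** The point holds as an inconsistency in an allocation rule that decides both treatment and arm membership. Under a literal 24-week limit, an on-window confirmed responder scanned on days 169 to 175 goes to Arm B; under the other text the same subject goes to Arm A. If all windows run late, the scan can reach day 189 and miss the 6-month limit as well.

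The frequency is unknown. The 7-of-15 figure describes permitted days, given a second scan on day 112; it is not a forecast of subjects.

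The conditional effect on Arm B is large: one such subject scored as a response takes the false-positive probability from 4.8% to 9.7% or 13.4%. This assumes that the subject stays in PR against the original baseline after ipilimumab starts, that the analysis applies the counting rule in Section 13.7.1 without the PD/SD restriction, and that the true rate among the others is 5%.

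**What to change.** 1. Reconcile the 24-week and 6-month statements in Section 2.7 with footnotes 7, 8 and 14 of the primary-treatment calendar. State when the 6-month clock starts and whether the limit carries the scan window, so that the same scans always give the same arm. Which limit should apply is for the investigators to decide.
2. Add one sentence to Section 13.7.1: a subject with two consecutive CR/PR scans on initial nivolumab is not counted as an Arm B conversion, whatever treatment followed, and is listed separately. This matches the PD/SD population in Sections 3.1.1 and 13.3. Say also whether such a subject stays in the Arm B denominator.

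The cost is one wording amendment and one analysis sentence. No new scans or subjects are needed.
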